10.6.4. Health- Related Quality of Life**St. George's Respiratory Questionnaire**

- The SGRQ contains 76 items grouped into three domains (Symptoms, Activity and Impacts). The domain score will be calculated as the sum of the weighted scores for the non-missing items within each domain, dividing by the maximum possible score for those non-missing items and multiplying by 100. The SGRQ total score will be calculated as the sum of the weighted scores from all 76 items and dividing by the maximum possible score for the SGRQ and multiplying by 100. This calculation is outlined in the developer's guide ([St. George's Respiratory Questionnaire Manual](#), 2009).
- If a subject has more than one response to a given item at a particular time point then the response will be taken as the average of the responses prior to calculating domain and total scores.
- If a subject has given both responses to a dichotomous question (yes/ no, true/false) the response to that question will be set to missing.
- If more than 25 % of items are missing from a domain, then the domain total will be set to missing. This equates to no more than two missed questions for the Symptom domain, no more than four missed questions for the Activity domain and no more than six missed questions for the Impacts domain. If any domain score is missing, then the total score will be set to missing.
- If the language of the SGRQ conducted during the study is different to the language used at Day 1, all SGRQ scores will be set to missing.
- The baseline SGRQ domain and total scores are those recorded on Day 1.
- A subject will be considered a 'responder' according to his SGRQ total score at each visit if the difference from the visit score to the baseline score was -4 units or lower. A subject will be

St. George's Respiratory Questionnaire

considered a 'non-responder' if the difference from the visit score to the baseline score was greater than -4 units.

- For the classification of responders, subjects with missing SGRQ total scores will be handled as detailed in Section [10.7.2.1](#) (Handling of Missing Responder).

CAT

- The CAT consists of eight items each formatted as a six-point differential scale: 0 (no impact) to 5 (high impact). A CAT score will be calculated by summing the non-missing scores on the eight items. If one or two items are missing, then the score for those items is set as the average of the non-missing items. If more than two items are missing, then the CAT score will be set to missing.
- The baseline CAT score will be that recorded on Day 1.
- A subject will be a responder if their on-treatment CAT score has decreased at least 2 units from baseline CAT total score.
- A subject will be considered a non-responder if their on-treatment CAT score has decreased by less than 2 units, has not changed, or has increased compared to baseline.
- For the classification of responders will be handled as detailed in Section [10.7.2.1](#) (Handling of Missing Responder).

Healthcare Resource Utilisation

- The total number of visits for each type of healthcare contact (telephone contacts, home visits (day), home visits (night), office/practice visits, urgent care/outpatient clinic visits, emergency room visits and the number of days in intensive care and in general hospital wards will be derived.

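### As written, the SGRQ total score is not adjusted for missed items although the domain scores are, so an incomplete questionnaire gives a total that is too low

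*SAP*

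**What the plan says.** SAP 10.6.4 (St. George's Respiratory Questionnaire) gives two scoring rules in consecutive sentences.

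- **Domains.** "The domain score will be calculated as the sum of the weighted scores for the non-missing items within each domain", followed by "dividing by the maximum possible score for those non-missing items and multiplying by 100". Numerator and denominator both cover answered items only.
- **Total.** The "sum of the weighted scores from all 76 items and dividing by the maximum possible score for the SGRQ", then scaled to 100. Neither part is restricted to answered items. The SAP adds: "This calculation is outlined in the developer's guide", citing the SGRQ manual.

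The same section sets the missing-item limits: "If more than 25 % of items are missing from a domain, then the domain total will be set to missing". It translates these into counts of "no more than two missed questions for the Symptom domain, no more than four missed questions for the Activity domain", and six for Impacts. The total is set to missing only when a domain score is missing. SAP 10.7.2.1 agrees, giving an absent domain as its example of a total that cannot be formed.

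A subject is an SGRQ responder "if the difference from the visit score to the baseline score was -4 units or lower", so a lower score is better. SAP 7.4.1 (Table 6) and 7.4.2 plan model-based treatment comparisons of both the total score and the responder proportion.

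**The concern.** The two rules treat the same missed item differently. In a domain score it drops out of both sums. In the total, taken at its word, it drops out of the numerator only, which has the same effect as recording the least impaired answer.

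This is also out of step with the rest of the SAP. A missing CAT item takes the mean of the answered items (10.6.4), a single trough FEV1 reading stands in for the pair (10.6.5), and a withdrawn subject becomes a non-responder (10.7.2.1).

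Missed items are foreseeable. Protocol 6.4.1 describes a self-completed questionnaire taking about 20 minutes, and SAP 10.6.4 itself sets a dichotomous question to missing when both answers are marked. Neither document says how often this happens.

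At stake are the SGRQ total-score and responder comparisons. Differences in completeness between baseline and a visit would appear as change in health status.

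**Working it through.** The documents contain no figure that rests on the total-score rule, so there is none to reproduce. The check applies the two formulas directly.

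**Inputs from SAP 10.6.4:** 76 items; limits of 2, 4 and 6 missed questions; responder threshold -4.

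**Assumptions, because the documents do not give these:** equal item weights; missed items resemble the answered ones; one missed question counts as one item; a score of 50 for illustration.

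**Step 1: how much may be missing.** 2 + 4 + 6 = 12 missed questions still leave a total.

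**Step 2: number of items implied by the limits.** A limit of m at 25% requires m/n ≤ 0.25 < (m + 1)/n.
- m = 2 gives n = 8 to 11.
- m = 4 gives n = 16 to 19.
- m = 6 gives n = 24 to 27.

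The sum is 48 to 57, whereas 25% of 76 is 19, not 12. The results below are therefore given for N = 76 and for N = 57 and 48.

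**Step 3: bias formula.** Let S be the pro-rated score on answered items and k the number missed out of N. The literal total is S × (N - k)/N, so the bias is -S × k/N.

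| Missed items k (S = 50) | N = 76 | N = 57 | N = 48 |
|---|---|---|---|
| 1 | -0.66 | -0.88 | -1.04 |
| 4 | -2.63 | -3.51 | -4.17 |
| 6 | -3.95 | -5.26 | -6.25 |
| 12 | -7.89 | -10.53 | -12.50 |
| Smallest k reaching -4 with no true change | 7 | 5 | 4 |

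With N = 76 the smallest k is 11 at S = 30 and 6 at S = 60. With the full 12 missed, any S of at least 4 × 76/12 = 25.3 reaches -4.

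**Step 4: internal consistency.** Three domain scores of 50 with 12 items missed give a total of 50 × 64/76 = 42.1 (39.5 for N = 57, 37.5 for N = 48), below every domain it summarises. Pro-rated like the domains, the total would be 50.

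**Step 5: direction (N = 76).**
- *Missed at the visit.* A true change from 50 to 47 (-3) with 2 items missed at the visit is computed as 47 × 74/76 - 50 = -4.24, a false responder.
- *Missed at baseline.* A true change from 50 to 45 (-5) with 2 items missed at baseline is computed as 45 - 50 × 74/76 = -3.68, a false non-responder.
- *Missed equally at both.* The change is multiplied by (N - k)/N, so most of the error cancels. With 12 missed at both visits, a true -4 becomes -4 × 64/76 = -3.37.

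**The case against.** The strongest objection is that the SAP nowhere says a missed item counts as zero. The total-score sentence can be read as the formula for a completed questionnaire, and the next sentence points to the developer's guide. If the guide handles missed items and the programmers follow it, the scores may be correct. This stands as a limit on the claim: a reader might infer that totals will certainly be wrong, and the documents do not establish that. It does not remove the point, because the SAP writes out a rule that differs between domains and total and is wrong if followed.

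Three further objections also stand.

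- **Direction and arms.** A reader might infer that the rule manufactures responders, or favours one arm. Step 5 shows that it can equally hide response. A treatment bias needs different completeness in the two arms, and the documents give no reason to expect that in a randomised, double-blind trial.
- **Frequency.** SAP 10.7.2 expects missing efficacy data mainly from whole visits or time points, and Protocol 4.3 (criterion 18) excludes subjects judged unlikely to complete questionnaires. Large numbers of missed items may be rare.
- **Importance.** Protocol 6.4 places the SGRQ outside the primary and key secondary endpoints, and SAP 10.11 makes comparisons other than the primary one exploratory. Domain scores are summarised separately (Tables 2.40 to 2.42) and SGRQ scores are listed (Listing 40), so a total below all its domains could be noticed.

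A reader might also conclude that 76 is a mistake. The SAP uses *items* for the 76 and *questions* for the limits, and never says that one question is one item. The figures cannot be reconciled as they stand, but the documents do not show which is wrong, or that either is.

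**Conclusion.** The point holds for the rule as written. The total-score formula lacks the restriction to answered items that the domain formula has, yet a total is kept with up to 12 missed questions. Followed literally, it understates the total in proportion to the missing weight.

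Under the stated assumptions, a single missed item matters only for subjects near the threshold. The permitted maximum of 12 missed items gives about twice the responder threshold with 76 items. The -12.5 figure, which a reader might take as the general worst case, applies only if there are 48 items.

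The effect on the trial is limited to the exploratory SGRQ total-score and responder analyses. Whether it occurs in practice depends on the developer's guide and on the pattern of missed items, neither of which the documents provide. The mismatch between items and questions is a matter of definition, not a proven error.

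**What to change.** In SAP 10.6.4, state that the SGRQ total is the sum of weighted scores for the non-missing items across all domains, divided by the maximum possible score for those same items, times 100. This is the rule already used for the domains, and under the assumptions above it removes the bias. Confirm the wording against the cited developer's guide before unblinding. If the guide prescribes another treatment of missed items, reconcile the SAP text with it.

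Define *item* and *question*, so that the 76 items, the 25% rule and the limits of 2, 4 and 6 can be applied in only one way.

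The cost is a sentence or two in the SAP and one line in the derivation program. No data collection changes.

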Subjects will be provided with a diary for daily completion in the morning throughout the run-in period and 24-week treatment period. Subjects will use the diary to record daily use of supplemental albuterol/salbutamol. All unscheduled COPD-related visits to a physician's office, urgent care facility, or emergency department, and COPD-related hospitalizations associated with the subject's condition will be recorded on the COPD-related healthcare resource utilisation assessment worksheet within the diary.

For determination of subject disposition, subjects will be considered to have completed the study upon completion of Day 169 (Visit 9). There is no plan to provide any of the active study treatments for compassionate use following study completion.

The Modified Intent-to-Treat (ITT) population will be the primary population of interest, and is defined as all randomised subjects who have received at least one dose of the randomised study medication during the Treatment Period.

Supplementary study conduct information not mandated to be present in this protocol is provided in the accompanying Study Procedures Manual (SPM). The SPM will provide the site personnel with administrative and detailed technical information that does not impact subject safety.

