3.2. Discussion of Design

A randomized, double-blind, placebo-controlled, parallel group study is a standard, well-established design to evaluate the efficacy and safety of an investigational drug. A placebo arm is included in this study to allow for an absolute assessment of efficacy and safety of the active treatment.

Duration of 24 weeks is considered adequate for assessment of lung function and symptoms in response to treatment intervention with bronchodilators, and is consistent with regulatory guidance on clinical studies in COPD. The choice of a lung function endpoint, trough FEV₁, as the primary efficacy endpoint is a robust, well established, and objective means of demonstrating bronchodilator efficacy and duration of effect at the end of 24 hours after dosing. Post-dose assessments of lung function on day 1 will provide for an assessment of treatment response over the 0 to 6 hour post-dose period which represents the beginning of the treatment effect.

A randomisation ratio of 2:1 will reduce the number of subjects randomised to placebo arm, as well as to reduce drop-outs.

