6.2.7. COPD Exacerbations

A COPD exacerbation will be defined as an acute worsening of symptoms of COPD requiring the use of any treatment beyond study medication or rescue albuterol/salbutamol. This includes requiring the use of antibiotics, systemic corticosteroids, and/or emergency treatment or hospitalization. COPD exacerbations will be recorded on the COPD exacerbation page of the eCRF.

Subjects who experience an exacerbation during treatment or run-in period requiring the use of any systemic/oral corticosteroids, with/without either prescribed or non-prescribed (self administered) antibiotics, and/or emergency treatment or hospitalisation will be withdrawn from the study and will not be allowed to re-screen. However, subjects who experience a COPD exacerbation/lower respiratory tract infection requiring only the use of antibiotics, either prescribed or non-prescribed (self-administered), may continue to participate in study.

COPD exacerbations are associated with the disease under study and will not be recorded as AEs unless the exacerbation meets the definition of a “serious” AE as defined in Section 6.3.5.2 of this protocol. Exacerbations that meet the definition of “serious” AEs will be recorded on the appropriate eCRF section and should be reported to GSK for all study subjects regardless of whether or not they are randomized to study medication.

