6.4.2. Healthcare Resource Utilisation

All unscheduled COPD-related visits to a Physician's office, urgent care facility, or emergency department, and COPD-related hospitalisations associated with the subject's condition will be recorded on the COPD-related healthcare resource use assessment worksheet within the diary, by the subject

At Visits 2 through 9 or at the Early Withdrawal Visit, the resource utilisation worksheet completed by the subject to record all health care contacts since the last visit will be reviewed by the investigator (or designee). The investigator (or designee) should ask the subject if any of the health care contacts recorded on the worksheets were due to COPD exacerbation. The investigator can refer to his/her records to verify or supplement information given by the subject if necessary.

If any unscheduled healthcare contact was due to a COPD exacerbation, then the COPD Exacerbation section of the eCRF must be completed.

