- Individual = Represents FL related to any displays of individual subject observed raw data.
- All the tables will be presented by treatment group.
- [1]: Absolute summary will be done on each at baseline, during each four weeks of treatment and over the entire 24-week treatment period. The change from baseline values will also be summarised by treatment, for each four weeks of treatment and the entire 24-week treatment period.
- [2]: A responder to TDI will be defined as a subject with TDI score of 1 unit or more
- [3]: The number and percentage of subjects reporting 0, 1, 2 or >2 on-treatment COPD exacerbations and the total number of exacerbations will be presented by treatment group. The number and percentage of exacerbations with each outcome category, the number and percentage of exacerbations leading to withdrawal and the number and percentage of exacerbations treated by oral/systemic corticosteroids, antibiotics, or which resulted in a visit to the emergency room or hospitalisation will also be presented. In addition, the exacerbation duration will be summarised.

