| 2.33. | NA | Modified ITT | DB2114634 6.31 | Summary of BDI Focal Score by Country/Region | | SAC |
| 2.34. | 2.28 | Modified ITT | DB2114634 6.32 | Summary of TDI Focal Score | | SAC[1] |
| 2.35. | NA | Modified ITT | DB2114634 6.33 | Summary of TDI Focal Score by Country/Region | | SAC |
| 2.36. | 2.29 | Modified ITT | DB2114634 6.34 | Analysis of TDI Focal Score, Repeated Measures | | SAC[1] |
| 2.37. | 2.30 | Modified ITT | DB2114634 6.35 | Summary and Analysis of Proportion of Responders According to TDI | | SAC |
| 2.38. | 2.31 | Modified ITT | DB2114634 6.36 | Summary of Baseline SGRQ Scores | | SAC |
| 2.39. | 2.32 | Modified ITT | DB2114634 6.37 | Summary of SGRQ Total Score | | SAC |
| 2.40. | 2.33 | Modified ITT | DB2114634 6.38 | Summary of SGRQ Symptoms Domain Score | | SAC |
| 2.41. | 2.34 | Modified ITT | DB2114634 6.39 | Summary of SGRQ Activity Domain Score | | SAC |
| 2.42. | 2.35 | Modified ITT | DB2114634 6.40 | Summary of SGRQ Impacts Domain Score | | SAC |

| Efficacy: Tables | | | | | | |
|------------------|--------------------|--------------|-------------------------------|---|-------------------|------------------------|
| IMCT No. | China Subgroup No. | Population | IDSL / TST ID / Example Shell | Title | Programming Notes | Deliverable [Priority] |
| 2.43. | 2.36 | Modified ITT | DB2114634 6.41 | Analysis of SGRQ Total Score | | SAC |
| 2.44. | 2.37 | Modified ITT | DB2114634 6.42 | Summary and Analysis of Proportion of Responders According to SGRQ Total Score | | SAC |
| 2.45. | 2.38 | Modified ITT | DB2114634 6.43 | Summary of Healthcare Resource Utilisation | | SAC |
| 2.46. | 2.39 | Modified ITT | DB2114634 6.44 | Summary of Baseline CAT Score | | SAC |
| 2.47. | 2.40 | Modified ITT | DB2114634 6.45 | Summary of CAT Score | | SAC |
| 2.48. | 2.41 | Modified ITT | DB2114634 6.41 | Analysis of CAT Score | | SAC |
| 2.49. | 2.42 | Modified ITT | DB2114634 6.42 | Summary and Analysis of Proportion of Responders According to CAT Score up to Week 24 | | SAC |
| 2.50. | 2.43 | Modified ITT | DB2114634 6.46 | Summary of On-treatment COPD Exacerbations | | SAC |
| 2.51. | 2.44 | Modified ITT | DB2114634 6.47 | Summary of Post-treatment COPD Exacerbations | | SAC |
| 2.52. | 2.45 | Modified ITT | DB2114634 6.48 | Summary and Analysis of Time to First On-treatment Exacerbation (days) | | SAC |
| Stats Appendix | | | | | | |

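### Healthcare contacts are summarised by arm as totals with no observed-time denominator or stated on-treatment window, so unequal drop-out can distort the comparison (minor)

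*SAP*

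**What the plan says.** Healthcare resource utilisation is a listed endpoint for UMEC versus placebo (Protocol Section 2; SAP 2.2). SAP 10.6.4 derives "The total number of visits for each type of healthcare contact" together with days in intensive care and on general wards. SAP Table 6 plans a summary and a listing with no model, and the display is Table 2.45, "Summary of Healthcare Resource Utilisation", in the Modified ITT population.

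On collection, Protocol 3.1 states: "Subjects will be provided with a diary for daily completion in the morning throughout the run-in period and 24-week treatment period". The contact worksheet sits in that diary. Protocol 6.4.2 sets the review times: "At Visits 2 through 9 or at the Early Withdrawal Visit, the resource utilisation worksheet completed by the subject" is checked by the site. The Visit 2 review therefore looks back over the run-in, and the last review is at Visit 9 or at early withdrawal. The follow-up call (Protocol 4.9) does not list healthcare use.

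On withdrawal, Protocol 4.5 takes a subject out of the study when study drug is permanently stopped. Subjects whose exacerbation needs systemic corticosteroids, emergency treatment or hospitalisation "will be withdrawn from the study and will not be allowed to re-screen" (Protocol 6.2.7).

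For exacerbations, SAP Table 5 note [3] says that subjects with 0, 1, 2 or more than 2 "on-treatment COPD exacerbations and the total number of exacerbations will be presented by treatment group". SAP 10.4.2.3 limits on-treatment events to onset from treatment start to one day after stop, and SAP 7.3.2.1 adds a Cox model for time to first exacerbation.

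**The concern.** A count depends on how long each subject was watched. Here watching stops at withdrawal, and some of the contacts being counted are what end it. A subject who leaves at Week 6 and one who completes 24 weeks contribute to the same summary with nothing to show the difference in exposure. If one arm loses more subjects, its totals are lower for that reason alone.

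The protocol gives some reason to expect unequal drop-out. Section 3.2 justifies 2:1 allocation by the smaller placebo arm "as well as to reduce drop-outs", which makes sense if placebo subjects are expected to leave more often. In that case the distortion works against showing a benefit of UMEC.

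For exacerbations, the Cox model takes account of follow-up. For healthcare use, no planned analysis does. Nor does SAP 10.6.4 say whether contacts made before the first dose belong in the totals.

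**Working it through.** **The plan's own figure.** Protocol 4.1 assumes 18% withdrawal among 288 randomised: 288 × (1 − 0.18) = 236.2, stated as approximately 236. It reproduces. No drop-out by arm, contact rate or exacerbation rate is stated, so everything below rests on assumed ranges. Ratios are placebo/UMEC per subject, so 2:1 allocation itself plays no part.

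**Case A: equal true rates, drop-out unrelated to events.** Splits satisfy (2u + p)/3 = 0.18, with u for UMEC and p for placebo. With a constant withdrawal hazard, the mean fraction of 24 weeks observed is w / (−ln(1 − w)). With equal rates, the apparent ratio is the ratio of these fractions. The last column is an outer bound, with every drop-out on Day 1: (1 − p)/(1 − u).

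| UMEC / placebo drop-out | Observed fraction | Apparent ratio | Day 1 bound |
|---|---|---|---|
| 18% / 18% | 0.907 / 0.907 | 1.00 | 1.00 |
| 15% / 24% | 0.923 / 0.875 | 0.95 | 0.89 |
| 12% / 30% | 0.939 / 0.841 | 0.90 | 0.80 |
| 10% / 34% | 0.949 / 0.818 | 0.86 | 0.73 |

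For example, 0.12/0.1278 = 0.939, 0.30/0.3567 = 0.841, and 0.841/0.939 = 0.90. Dividing by observed time returns 1.00 in every row.

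**Case B: the events force withdrawal.** Let λ be the event rate per year, q the share of events that force withdrawal, h the hazard of other drop-out, T = 24/52 year and k = qλ + h. Events per subject are λ(1 − e^(−kT))/k, and the triggering event is counted. Assumed values: λ for UMEC 0.3 to 1.0, q 0.5 to 1, h = 0.2 in both arms.

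- Largest attenuation of a true ratio of 1.5 (λ = 1.0, q = 1). UMEC: k = 1.2, 0.354 events per subject. Placebo: k = 1.7, 0.480. The ratio reads 0.480/0.354 = 1.35.
- Smallest (λ = 0.3, q = 0.5). UMEC: k = 0.35, 0.128. Placebo: k = 0.425, 0.189. The ratio reads 1.48.
- Over the whole range, 1.25 reads 1.19 to 1.24 and 2.0 reads 1.64 to 1.93. None falls below 1, and per subject-year each returns the true ratio.

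**Case C: run-in contacts.** A run-in of 7 to 14 days is 7/175 = 4.0% to 14/182 = 7.7% of a completer's collection time. If both arms have the placebo rate before dosing, a true ratio of 1.5 reads (175 × 1.5)/(7 × 1.5 + 168) = 1.47 with 7 days and (182 × 1.5)/(14 × 1.5 + 168) = 1.44 with 14 days. At a true ratio of 1 nothing changes.

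**When could the ordering reverse?** In Case A terms, the true ratio times the apparent ratio must fall below 1. At 12%/30%, 1.1 × 0.896 = 0.99, which is just below 1. At 10%/34%, 1.1 × 0.862 = 0.95, but 1.25 × 0.862 = 1.08. At constant hazard, reversal therefore needs a true ratio close to 1 and differential drop-out unrelated to the events.

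**The case against.** The strongest reply is that little rests on these displays. Healthcare use has no model or p-value, SAP 10.11 treats comparisons beyond the primary endpoint as exploratory, and exposure, disposition and withdrawals over time are all shown by arm. That stands, and it limits the severity. It does not supply the missing denominator: a reader of Table 2.45 cannot combine those displays into a rate.

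Second, SAP 10.4.1 classifies events by default as pre-, on- or post-treatment, so a window arguably exists. But 10.6.4 does not invoke that rule, and only one healthcare table is planned, not split by phase. The table shell is not in the documents, so the exact presentation cannot be seen.

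Three stronger readings are tempting, and the documents do not support them:

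- *The arm with more drop-outs will look as if it uses less care.* A forced withdrawal is triggered by an event that is itself recorded, and the worksheet is reviewed at the Early Withdrawal Visit. Drop-out of that kind shrinks a difference without reversing it (Case B).
- *Exacerbation totals are equally affected, run-in included.* They are restricted to on-treatment onset, a run-in exacerbation bars randomisation (Protocol 4.4), and per-subject counts and a Cox analysis accompany them.
- *Drop-out of 12% and 30% is implied by the documents.* Those values also fit a 21% rate under 1:1 allocation, but that rate is superseded, and two equations in two unknowns are no corroboration. The split is one assumption among several.

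One uncertainty cuts the other way. SAP 10.7.1 admits data from a standalone Early Withdrawal Visit to tables only through worst-case post-baseline summaries, and none exists for healthcare use. Read literally, the admission that caused a withdrawal could be left out. Protocol Table 5 note 7 has contacts entered as they arise, so this reading is not certain, but the SAP should settle it.

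**Conclusion.** The point holds as a minor one. Healthcare use is summarised by arm without adjustment for observed time and without a stated on-treatment window, while collection begins in the run-in and ends at withdrawal. Unequal drop-out can therefore understate use in the arm that loses more subjects.

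With drop-out unrelated to events and constant hazard, the understatement runs from nothing to about 14% over the assumed splits. With event-forced withdrawal it is an attenuation, provided the triggering contact is counted. The run-in dilutes and favours neither arm. For the on-treatment exacerbation total the missing denominator matters less, because the Cox analysis already allows for follow-up. All sizes depend on assumed drop-out and event rates. The primary conclusion is unaffected.

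**What to change.** In SAP 10.6.4, state that contacts and hospital days are counted from the first dose to the date of completion/withdrawal already derived in SAP 10.6.1, and that contacts first reviewed at an Early Withdrawal Visit are included.

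In Table 2.45 (China subgroup 2.38), keep the totals and add, by arm, total observed time and the rate per subject-year: sum of contacts divided by sum of observed days, times 365.25. Show run-in contacts separately. In Table 2.50 (China subgroup 2.43), add a per-subject-year row for the on-treatment exacerbation total, using the SAP 10.4.2.3 window.

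Footnote two limits: forced withdrawal still truncates repeat events, and a pooled rate assumes a roughly constant event rate, so it too can be attenuated if high-risk subjects leave early.

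The cost is SAP wording and a few extra rows in two tables per analysis set. It uses dates already derived or collected and needs no change to trial conduct.
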